8.2.3 Visual Field Testing

Visual field sensitivity will be assessed at scheduled time points post-treatment, using Goldmann visual field area and Humphrey 10-2, in subjects with adequate fixation to allow reliable testing.

8.2.4 Fluorescein Angiography

Fluorescein angiography will to be assessed at scheduled time points to examine the circulation of the retina and choroid using a fluorescent dye and a specialized camera. The procedure involves pupil dilation and IV injection of the dye, sodium fluorescein. An angiogram is obtained by photographing the fluorescence emitted after illumination of the retina with blue light at a wavelength of 490 nanometers.

The fluorescein dye also appears in the patient urine, causing the urine to appear darker, and sometimes orange. It can also cause discoloration of the saliva and the skin will appear yellow for several hours after the angiogram.

8.2.5 Autoflourescence

Fundus autofluorescence images specifically assess the health of the retinal photoreceptors (RODS and CONES) and the retinal layer which provides nutrition to the rods and cones (the retinal pigmented epithelium - RPE). FAF is effective because it can document metabolic change from the accumulation of toxic fluorophores in the retinal pigment epithelium. The test may require pupil dilation but does not require injection of any dye.

8.2.6 Exploratory Visual Assessments

Best Corrected Visual Acuity

Trial frame refraction is the gold standard in obtaining the most accurate refractive error in low vision patients. It involves the use of a trial frame, loose lenses and specialized low vision eye charts that are different from the eye charts used in a regular eye examination. These special low vision eye charts contain different-sized letters or numbers that can help determine the sharpness or clarity of the subject's distance vision. Performed properly, the examiner obtains not only the refractive error, but additional potentially essential information, such as the level and quality of visual acuity, sensitivity to blur, effects of glare and the quality of fixation. The optical theory involved is the same as when refracting the normal eye, but special adjustments in lens selection, presentation strategy, and "just noticeable difference", are incorporated for low vision patients. These adjustments usually include large lens increments and special techniques for exploring and refining cylinders.

The Freiburg Visual Acuity & Contrast Test (FrACT) assesses visual acuity and contrast sensitivity. It is a free computer program that uses computer graphics capabilities and psychometric methods to provide automated, self-paced measurement of the visual acuity and contrast sensitivity.

Contrast Sensitivity

A contrast sensitivity test measures the ability of a subject to distinguish between finer and finer increments of light versus dark (contrast). Contrast provides critical information about edges, borders, and variations in luminance. Their usefulness as a measure for predicting performance on many real world tasks and their sensitivity to a range of visual disorders has led to the development of several easily-administered clinical tests of contrast sensitivity. Examples of tests for contrast sensitivity function include the Pelli Robson (P-R) Contrast Sensitivity Chart, the Mars Letter Contrast Sensitivity Test, and mixed contrast eye charts.

Low Luminance

Low Luminance Visual Dysfunction Testing has been shown to be a predictor of subsequent visual acuity loss. Some believe that it is a better predictive factor for how much the disease has progressed than standard visual acuity. Examples of testing include using a wire-rimmed 2.0-log-unit neutral density filter or a NoIR U23 fitter (4% transmission) grey lens during visual acuity or visual field testing.

Color Vision Testing

Quantitative measurement of color vision is an important diagnostic test used in evaluating deficient color vision. The exploratory tests of interest are designed to correctly identify all (congenital and acquired) color deficiencies, no matter how slight. They may include large cap sizes, which give more information about color vision function both in normally sighted

and low vision individuals. Examples include the D15 Large Caps Test and the use of pseudoischromatic plates.

Visual Field Testing

Visual Field testing is an important test in measuring a subject's peripheral vision. In patients with RP, the California Central Visual Field Test and Tangent Screen Perimetry Testing allows for a flexible head posture when fixating on targets. This flexibility may give a more accurate assessment and provide more information about steadiness of fixation and degrees of remaining constricted field of vision especially when the remaining vision or an island of vision in severely impaired subjects is eccentrically located. The Tangent Screen can assess up to 60 degrees of the visual field when used at a test distance of 1 meter, allowing for identification and mapping of peripheral islands of vision.

Activities of Daily Living (ADL)

Assessing changes in the day-to-day functional changes/improvements is considered to be one of the most important assessments for subjects with low vision. There are several instruments that have been developed for this purpose that may be useful in the low vision patient population in this study.

The National Eye Institute (NEI) VFQ-25 survey measures the influence of visual disability and visual symptoms on generic health domains such as emotional well-being and social functioning, in addition to task-oriented domains related to daily visual functioning. A number of clinical studies have used either the 51 or the 25-item version of the NEI-VFQ across a number of chronic ocular conditions. The VFQ-25 takes approximately 10 minutes on average to administer in the interviewer format.

The Activity Inventory (AI) developed by [name] at Johns Hopkins organizes everyday activities into a hierarchical framework. Within this structure tasks refer to very specific cognitive and motor activities. Examples of tasks include cutting food, reading recipes, setting stove and oven dials, and measuring ingredients. Goals refer to the reasons for performing tasks. For example, cutting food, reading recipes, measuring ingredients, etc. are all tasks that are performed with the goal of cooking daily meals. Goals, in turn, are organized under objectives. The Activity Inventory has three objectives: living independently, social interactions, and recreation. Fifty goals are listed under those three objectives, and 450 tasks are under the fifty goals, so it is a rather lengthy test.

The Low Vision Visual Functional Questionnaire (LV-VFQ48 is a valid and reliable questionnaire that may be administered by telephone to capture changes in patients' self-report of their difficulty reading and performing other daily living activities affected by visual impairment before and after rehabilitation. In our case, the intervening "rehabilitation" would instead be the hRPC treatment.

The Functional Independence Measure (FIM) scale assesses physical and cognitive disability. Items are scored on the level of assistance required for an individual to perform activities of daily living. The scale includes 18 items, of which 13 items are physical domains and 5 items are cognition items. The scale can be administered by a physician, nurse, therapist or layperson. It takes 1 hour to train a rater to use the FIM scale, and 30 minutes to score the scale for each patient. The FIM scale has been used clinically to measure the patient's progress and assess rehabilitation outcomes.

The Prosthetic Low Vision Rehabilitation (PLoVR) Curriculum was developed for use in the Argus clinical trials because available standardized visual functioning questionnaires included few if any items that can be accomplished with rudimentary vision. The Functional Low Vision Observer Rated Assessments were deployed in these studies of retinal implants for RP patients and may be of value in studies of hRPC.

Reading Assessments

As for ADL, a number of tools have been developed to assess reading skills in the low vision population.

The Minnesota Low Vision Reading Test (MNRead) consists of single simple sentences with equal numbers of characters. The test is computer-based, although a printed card version is also available. This test is aimed at low-vision readers. The format of the MN Read Test allows it to be performed rapidly and easily. It focuses attention on impairments of resolution and is useful for determining the impact of print size on reading performance. It can be used to establish the critical print size - the smallest font where maximal rate of reading can be accomplished and is useful for estimating the response to magnification.

The continuous-text MNREAD eye charts extend past the reach of traditional eye exams because of their capability to measure the impact of eye conditions on reading. The traditional letter charts are designed to measure acuity and contrast sensitivity, but do not provide direct information about reading vision. The MNREAD chart extends the capability of eye examinations by measuring the patient's reading acuity, maximum reading speed, and critical print size, which is the smallest print size that supports the maximum reading speed.

9.0 SAFETY CONSIDERATIONS

9.1 Adverse Events

An AE is defined for this study as any untoward medical occurrence in a subject who is administered clinical study material. The occurrence of this event does not necessarily have a causal relationship with study product. An AE can therefore be any unfavorable and unintended sign (including an abnormal laboratory finding), symptom, or disease temporally associated with the use of a study (investigational) product, whether or not related to the study product.

Examples of an AE include:

- Exacerbation of a chronic or intermittent pre-existing condition, including either an increase in frequency or intensity of the condition
- Significant or unexpected worsening or exacerbation of the condition/indication under study (RP)
- A new condition detected or diagnosed after study product administration even though it may have been present prior to the start of the study
- Signs, symptoms, or clinical sequelae of a suspected overdose of either study product or a concurrent medication
- Pre- or post-treatment events that occur as a result of protocol-mandated procedures
- Antibody development

An AE does not include:

- Medical or surgical procedures (e.g., colonoscopy or biopsy); the medical condition that leads to the procedure is an AE
- Social or convenience hospital admissions where an untoward medical occurrence did not occur
- Day-to-day fluctuations of a pre-existing disease or conditions present or detected at the start of the study that do not worsen
- The disease/disorder being studied (RP), or expected progression, signs, or symptoms of the disease/disorder being studied unless more severe than expected for the subject's condition

All AEs that occur after informed consent is signed will be recorded in the source documents and on the appropriate CRF page. The information to be collected includes the nature, date and time of onset, intensity (mild, moderate, severe, life-threatening, death), duration, causality (relationship to investigational product), and outcome of the event. Even if the AE/SAE is assessed by the Investigator as not reasonably attributable to study product, its occurrence must be recorded in the source documents and on the appropriate page of the CRF.

Treatment-emergent AEs will be defined as AEs that occur after the treatment with jCell.

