1.0 INTRODUCTION

1.1 Background

1.1.1 Retinitis Pigmentosa

Retinitis pigmentosa (RP) refers to a group of inherited diseases causing retinal degeneration. The cell-rich retina lines the back inside wall of the eye. It is responsible for capturing images from the environment. People with RP experience a gradual decline in their vision because photoreceptor cells (rods and cones) die. Forms of RP and related diseases include Usher syndrome, Leber's congenital amaurosis, rod-cone degeneration, Bardet-Biedl syndrome, and Refsum disease, among others.

In most forms of RP, rods are affected first. Because rods are concentrated in the outer portions of the retina and are triggered by dim light, their degeneration affects peripheral and night vision. When the more centrally located cones - responsible for color and sharp central vision - become involved, the loss is in color perception and central vision. Night blindness is one of the earliest and most frequent symptoms of RP.

RP is typically diagnosed in adolescents and young adults. The classic clinical sign of the disease is the presence of dark deposits in the retina. The main risk factor is a family history of retinitis pigmentosa. It is an uncommon condition affecting about 1 in 4,000 people or roughly 100,000 individuals in the US¹. Cases of RP are associated with a wide variety of known gene mutations, with new mutations still being discovered. The mutations can be inherited from one or both parents, or occur spontaneously; the pattern of inheritance can be autosomal recessive, autosomal dominant, X-linked or mitochondrial.

There is no effective treatment for RP; once photoreceptors are lost, they do not regenerate. The rate of deterioration of vision varies from person to person, with most people with RP legally blind by age 40. People with RP also often develop cataracts at an early age, or swelling of the retina (retinal edema). Numerous breakthroughs in the treatment of cataract and corneal disease have greatly decreased the incidence of blindness from these causes. In contrast, treatment of retinal and optic nerve disease is more limited, with these conditions now representing major causes of incurable visual loss and a significant unmet medical need.

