3.2 Endpoints

3.2.1 Efficacy Endpoints

The response to jCell injection will be assessed based on the following:

- Change in BCVA at scheduled time points compared to baseline as well as contralateral eye. Acuity testing will be standardized using E-ETDRS.
- Changes in ellipsoid zone (EZ) band width at specified time points based on Spectral Domain Optical Coherence Tomography (OCT) compared to baseline as well as contralateral eye.
- Changes in electroretinogram (ERG) physiologic analysis compared to baseline as well as contralateral eye.
- Visual field sensitivity at scheduled time points post-treatment, using Goldmann visual field area and Humphrey 10-2, in subjects with adequate fixation to allow reliable testing.

In addition to the assessments listed above, a number of visual assessments that may be more appropriate for low vision subjects have been recommended by low vision experts. While BCVA is the gold standard for vision assessment, it is clear that this test is not particularly CONFIDENTIAL 16 of 41

relevant or accurate for subjects with very poor vision (legally blind). As there is little experience with our treatment approach, and subjects with very advanced vision loss are included in Cohort 1, it is planned to try some non-invasive assessments in subgroups of subjects, dependent upon the subjects' visual range and capabilities. These assessments include but are not limited to trial frame refraction, testing for contrast sensitivity (examples include Pelli-Robson Contrast Sensitivity Chart, Mars Letter Contrast Sensitivity Test, low luminance testing and mixed contrast eye charts); testing for color vision changes (e.g. D15 large caps, pseudoisochromatic plates), FrACT, California Central Visual Field Test, Tangent Screen Perimetry, ADL questionnaire (e.g. VFQ25, activity inventory, Low Vision Visual Functional Questionnaire [LF-VFQ], Function Independence Measures [FIM], Prosthetic Low Vision Rehabilitation [PVoVR]) and testing for changes in reading ability (e.g. Continuous Text Reading, MN Read). The goal of exploring some or all of these assessments is to develop a qualified, quantitative tool or set of tools for assessing post-treatment changes.

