3.2.2 Safety Endpoints

The primary goal of the study is to evaluate the safety and tolerability of jCell injection: The criteria that will be used to establish safety include:

- Slit-lamp findings, i.e., anterior chamber cell or flare; acute cataract development or progression in phakic patients, vitreous haze.
- Absence of tumor formation, overt immune rejection, decrease in BCVA attributable to treatment
- Absence of clinically significant, persistent increase in intraocular pressure (>10 mm Hg above baseline or IOP > 25 mm Hg), clinically significant epiretinal membrane, retinal detachment, neovascularization, or endophthalmitis
- No clinically significant adverse events attributable to investigational product (jCell) injection
- Patient comfort (no intolerable pain related to procedure)

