8.2.1 BCVA

BCVA will be tested at scheduled time points in both the treated and the contralateral eye. Visual acuity will be measured with the electronic visual acuity testing algorithm (E-ETDRS). E-ETDRS testing will be conducted using the electronic visual acuity tester (EVA). Based on estimates of 95% confidence intervals, a change in visual acuity of 0.2 logMAR (10 letters) from a baseline level is unlikely to be related to measurement variability using either the E-ETDRS or the S-ETDRS visual acuity testing protocol.

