8.2.2 Electroretinogram (ERG)

ERG examinations will be performed according to ISCEV standards and standardized among clinics to minimize difference between centers: briefly, patients are dark adapted for 30 min, electrodes attached under dim red illumination (dark room safe light). ERG responses will be recorded using single scotopically-balanced dim blue and red light flashes, and bright white flashes per detailed protocol. ERG at 6, 12 months are compared to pre-injection in terms of 1) a-wave amplitude, 2) b-wave amplitude, 3) time from flash onset to a wave trough and 4) time from flash onset to b-wave peak. In individual patients significantly faster deterioration of injected eye by ERG parameters and BCVA will halt further enrollment, although the latter measure is likely to be the more informative.

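### The categorical BCVA tables count only gains, no BCVA table sits in the safety set, and declines among eyes already off-chart at baseline score as no change

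*Protocol*

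**What the plan says.** The primary objective in both documents is safety and tolerability. Protocol 3.2.2 lists absence of a "decrease in BCVA attributable to treatment" among the criteria for establishing safety, without a number. Protocol 8.2.1 gives the only numeric acuity limit: "a change in visual acuity of 0.2 logMAR (10 letters) from a baseline level is unlikely to be related to measurement variability".

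Protocol 9.1 counts "Significant or unexpected worsening or exacerbation of the condition/indication under study (RP") as an adverse event and excludes "expected progression, signs, or symptoms of the disease/disorder being studied unless more severe than expected for the subject's condition". Protocol 8.2.2 says that significantly faster deterioration of the injected eye on ERG and BCVA will halt further enrolment, "although the latter measure is likely to be the more informative".

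On the analysis side:

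- SAP 9.1 and the Appendix C shells summarise letters correct (100 minus letters missed) and change from baseline. They add proportions of eyes gaining at least 5, 10 and 15 letters at any post-baseline visit and at Months 3, 6, 9 and 12 or early termination. No shell has a row for letters lost.
- SAP 9.1 assigns zero letters correct to a subject without a number score, naming CF, HM and NLP as examples.
- All BCVA tables are numbered 14.2.1.x, as efficacy tables in the ITT population. SAP section 10 and the 14.3 table list contain none.
- Listing 16.2.6.1 gives each eye's acuity measurement by visit.

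**The concern.** A loss of acuity after an intravitreal cell injection is one of the harms this study exists to detect, and the protocol names it as a safety criterion. A reader of the categorical tables sees how many eyes gained but cannot see how many lost. An eye that lost 15 letters looks the same there as an eye that did not change.

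In the most impaired eyes the problem extends to all the BCVA summaries. Cohort 1 admits eyes down to HM, and SAP 9.1 puts every off-chart level at the same score. An eye going from HM to NLP has lost its remaining form and light vision, yet it enters the mean, median and minimum change as zero.

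Dose cells hold four or three subjects, so one such eye is 25% or 33% of a cell.

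**Working it through.** The plan states no figure to reproduce: SAP section 4 says the sample size had no formal statistical basis.

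**1. Rows in the categorical tables (SAP Appendix C).** 3 tables × 5 time blocks (any post-baseline, Months 3, 6, 9, and 12 or early termination) × 3 thresholds = 45 gain rows. Loss rows: 0.

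**2. The off-chart floor (SAP 9.1; Protocol 4.1, criterion 4).** An eligible off-chart baseline is CF or HM. The possible declines are CF to HM, LP or NLP and HM to LP or NLP, which makes five. Each scores 0 − 0 = 0 letters. SAP 9.1 does not name LP; I assume it is scored like the others. Only Cohort 1 can be affected, so the range is 0 to 14 subjects of 28.

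**3. On-chart eyes that fall off-chart.** These are not scored zero; the change is minus the baseline score. For assumed baselines of 5, 20 and 35 letters correct, a fall to HM or NLP gives −5, −20 and −35. A baseline of 1 to 9 letters gives a change of −1 to −9, so this fall would not reach a 10-letter loss row. Letter rows alone are therefore not enough, and a category shift is needed as well.

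**4. Where a loss can be seen under the present plan.**

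| Decline | Categorical tables | Mean, median, minimum change | Listings |
|---|---|---|---|
| On-chart, still on-chart | no row | yes | yes |
| On-chart to off-chart | no row | yes | yes |
| Off-chart, further down | no row | no (scores 0) | yes |

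The minimum shows the worst eye in a cell, not how many eyes passed a limit. The other listing source is the vision-change item in the physical examination listing. It covers Days 1, 7 and 28 and Months 3, 6 and 12, which is 6 of the 13 post-injection BCVA visits in Protocol Table 2. SAP 10.5 keeps physical examination results in listings only.

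**5. How many chance losses the new rows would show.** Assume the 10 letters in Protocol 8.2.1 are the two-sided 95% limit for the difference between two tests.

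- SD of a difference = 10 / 1.96 = 5.10 letters.
- With Normal error and no true change, the chance of a loss of at least 10 letters at one fixed visit is 2.5%; 0.025 × 28 = 0.7 eyes.
- At any of 13 visits, with the baseline error shared, simulation of 1,000,000 eyes gives 16.7%; 0.167 × 28 = 4.7 eyes.

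By symmetry the same figures hold for chance gains, which the tables do count. The 16.7% applies only to the three any-visit rows for at least 10 letters. All these counts are upper figures, because an eye without a number score has no letter noise.

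**The case against.** The strongest reply is that losses are not hidden. Tables 14.2.1.1 and 14.2.1.5 give mean, median and minimum change, and in a cell of three or four subjects one large on-chart loss is plain. Protocol 8.1.5 schedules ophthalmic procedures to find eye events that usual reporting may miss. SAP 10.7 tabulates the slit lamp, IOP, B-scan, fundus and other findings whatever their AE status. The DSMB reviews safety data at the Cohort 1 escalations. The halt rule in Protocol 8.2.2 has no number, but it does not depend on an AE record. All of this stands, and it limits the point to presentation and scoring. It does not supply a count of eyes that lost vision, and it does not lift the off-chart floor in the summaries.

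A reader might infer more: that the 9.1 exclusion, having no letter threshold, lets an unmasked investigator keep study-eye losses out of the AE tables, and that any error must run toward under-counting harm. The documents do not support that. Section 9.1 counts worsening that is either significant or unexpected. It also requires recording whatever the attribution: "Even if the AE/SAE is assessed by the Investigator as not reasonably attributable to study product, its occurrence must be recorded", although that duty begins once an event is classed as an AE. "The rate of deterioration of vision varies from person to person", so judging what is expected for a subject is difficult, but error can go either way, since an unmasked investigator may also report ordinary progression as an AE. The defaults in SAP 10.2 are conservative: a missing relationship counts as related, and an onset that cannot be placed counts as treatment-emergent. Thresholds may also sit in the procedure manual, which is not among these documents.

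A second tempting reading, that every off-chart decline scores zero, is wrong for eyes that start on-chart, as step 3 shows.

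**Conclusion.** The point holds as a defect of tabulation and scoring. The categorical BCVA tables have 45 gain rows and no loss rows, although loss of BCVA is a stated safety criterion, and no BCVA table is presented with the safety data. For Cohort 1 study eyes already off-chart at baseline, all five possible declines read as zero change in every BCVA summary table and can be found only in listings.

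The number of eyes affected by the floor lies between 0 and 14. It depends on how many enter at CF or HM, which the documents do not say. They also give no rate of true losses, so no claim is made about how often one would go unnoticed. The noise figures rest on the assumed reading of the 10-letter limit and on equal variability in both cohorts. The second is doubtful, because Protocol 3.2.1 says BCVA is not particularly "relevant or accurate for subjects with very poor vision (legally blind").

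A compulsory AE record for a BCVA loss above a set limit is a matter of judgment. Its absence from 9.1 is not an error in the plan.

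**What to change.** 1. Add rows for losses of at least 5, 10 and 15 letters to Tables 14.2.1.3, 14.2.1.4 and 14.2.1.6, at the same time points as the gain rows, including any post-baseline visit, and for both eyes.
2. Add a by-eye shift table, or a category-drop row, from baseline to each visit using the levels number score, CF, HM, LP and NLP. Take the level from the recorded acuity measurement, not from the derived letter score. State how LP is scored.
3. Present both for the Safety population and list them in the 14.3 set. If the Safety and ITT populations coincide, one table can serve both, as SAP 7.3 already allows for demographics.

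No new visit, test or CRF page should be needed, provided the form records the off-chart level, as SAP 9.1 implies. The cost is modest programming and some chance losses on display: about 0.7 of 28 eyes at a fixed visit and 4.7 of 28 at any of 13 visits for at least 10 letters. The fellow-eye rows show how much of this is noise or natural course.

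Optionally, the sponsor could amend 9.1 to require an AE record for a confirmed 10-letter loss or category drop, with causality as a field. That would bring some noise into the AE tables, and reasonable statisticians would differ on it.
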